7.2.2 Laboratory Abnormalities

To the extent possible, all new or worsening laboratory abnormalities observed during the course of the study will be included under a reported AE describing a clinical syndrome (e.g., elevated blood urea nitrogen and creatinine in the setting of an AE of "renal failure" or elevated ALT/AST in the setting of an AE of "hepatitis"). In these cases (e.g., an AE of renal failure), the laboratory abnormality itself (e.g., elevated creatinine) does not need to be recorded as an AE.

An abnormal laboratory value that is not already associated with an AE (e.g., symptoms or diagnosis) is to be recorded as an AE only if an action on the study drug or concomitant medication is made as a result of the abnormality, if intervention or management of the abnormality is required, or at the discretion of the Investigator.

Patients experiencing laboratory abnormalities will be assessed and appropriate evaluations performed until all parameters have returned to baseline levels, or are consistent with the patient's then-current physical condition.

7.2.3 Serious Adverse Events

Instructions for reporting Serious Adverse Events are found on Page 4.

A written report of all SAEs and deaths that occur between the signing of the ICF and 28 days after administration of the last dose must be submitted to the IRB/EC and Forma Therapeutics Pharmacovigilance. All SAEs must be reported to Forma Therapeutics Pharmacovigilance within 24 hours for a determination of expedited reporting to the relevant regulatory health authority, as

described in Section 7.5. In all SAE reports, the Investigator will advise whether or not the SAE is judged to be related to study drug administration.

Serious AEs and deaths that occur more than 28 days after administration of the last dose and are not reasonably associated with study drug do not require reporting per the instructions given below. All SAEs that are judged by the Investigator to be at least possibly related to study drug administration must be reported to the Sponsor or its designee regardless of how much time has elapsed since the last exposure to study drug. All nonserious AEs must be communicated to the appropriate IRB/EC and/or reported in accordance with local laws and regulations.

7.2.4 Adverse Events of Special Interest

As described in Section 5.5.3, adverse events potentially associated with liver injury have been identified as AESI. These AESI (regardless if serious or non-serious) include the following:

- a. All events of Grade 2 or higher elevations in ALT, AST, or total bilirubin in patients with normal LFTs at baseline; in patients with elevated LFTs at baseline, one Grade shift or higher in ALT, AST, or total bilirubin;
- b. Any hepatic adverse event, e.g., acute hepatitis, cholestatic hepatitis, cholestasis, or hepatic insufficiency

AESI occurring from time of first dose through 28 days after last dose must be reported as outlined below:

- a. Report to Forma Therapeutics Pharmacovigilance within 24 hours of knowledge of event
- b. If the event meets both AESI and SAE criteria, complete both the SAE and AESI form
- c. If the event is non-serious, complete the AESI form alone

Relevant forms (AESI, SAE, or both) should be submitted via fax ([contact]) or email ([contact]) to Forma Therapeutics Pharmacovigilance.

7.2.5 Reporting of Pregnancies

If a patient, or the female partner(s) of a male study patient, becomes pregnant during the course of the study, the Investigator or site personnel must notify Forma Therapeutics Pharmacovigilance (see Page 4 for contact details) within 24 hours of the Investigator or site personnel becoming aware of the pregnancy. If an SAE occurs in conjunction with the pregnancy, then the reporting time frame for an SAE (within 24 hours) must be met.

The Sponsor's representative will provide instructions on how to collect pregnancy information as per the pregnancy reporting guidelines. The pregnancy reporting period begins upon administration of the first dose of FT-2102, and pregnancies will be reported until 90 days after the last dose of FT-2102. A final Pregnancy Report Form should be completed when outcome of the pregnancy is known. Any follow-up information on the outcome of the pregnancy should be forwarded to the Sponsor.

7.2.6 Disease Progression

If progression of the underlying disease (i.e., the condition being treated with study drug) might be reasonably anticipated given the nature and severity of the underlying disease, then progression of the underlying disease per se will not constitute an AE. However, if the progression of the underlying disease meets the criterion for "serious" categorization of AEs (e.g., the underlying disease results in death or hospitalization), then the progression of underlying disease should be reported as an SAE (See Section 7.2.3).

7.2.7 Overdoses

Overdoses during the course of the study (whether symptomatic or not) should be reported by the Investigator or qualified designee as a protocol violation within 24 hours of the Investigator or qualified designee first becoming aware of the overdose. If an overdose results in an AE, the eCRF AE page should be completed, and source documents included. If the overdose results in an SAE, then SAE reporting should be followed using the specific eCRF pages with overdose information entered in the narrative section. All available clinical information relevant to overdose, including signs and symptoms, laboratory findings, and therapeutic measures or treatments administered, should be summarized and discussed. The overdose should also be captured on the appropriate FT-2102 exposure eCRF.

7.3 Classification of Adverse Events by Severity

The severity refers to the intensity of the AE. The Investigator must categorize the severity of each AE according to the NCI CTCAE version 4.03 (see Appendix 4). CTCAE guidelines can be referenced at the following website: http://ctep.cancer.gov/reporting/ctc.html.

For any term that is not specifically listed in the CTCAE scale, intensity will be assigned a grade of one through five using the following CTCAE guidelines:

Grade 1: Mild; asymptomatic or mild symptoms, clinical or diagnostic observations only; intervention not indicated

Grade 2: Moderate; minimal, local or noninvasive intervention indicated; limiting age-appropriate instrumental activities of daily living

Grade 3: Severe or medically significant but not immediately life-threatening; hospitalization or prolongation of hospitalization indicated; disabling; limiting self-care activities of daily living

Grade 4: Life-threatening consequences; urgent intervention indicated

Grade 5: Death related to AE

7.4 Classification of Adverse Events by Relationship to Study Drug Administration

The relationship of each AE to the study drug administration will be assessed by the Investigator; after careful consideration of all relevant factors such as (but not limited to) the underlying study indication, coexisting disease, concomitant medication, relevant history, pattern of the AE, temporal relationship to the study medication and dechallenge or rechallenge according to the following guidelines:

YES (possible, probably, or definitely related): there is a reasonable possibility that the study drug caused the event; one or more of the following criteria apply:

- The event follows a reasonable temporal sequence from administration of study drug
- The event could not be reasonably attributed to the known characteristics of the patient's clinical state, environment, or toxic factors or other modes of therapy, administered to the patient
- The event follows a known pattern of response to study drug
- The event disappears or decreases on cessation or reduction in dose of the study drug. In some situations, an AE will not disappear or decrease in intensity upon discontinuation of the study drug despite other clear indications of relatedness

NO (unlikely, probably not related, or definitely not related): There is no reasonable possibility that the study drug caused the event; one or more of the following criteria apply:

- The event does not follow a reasonable temporal sequence from administration of study drug
- The event could be reasonably attributed to the known characteristics of the patient's clinical state, concurrent illness, environment, or toxic factor or other modes of therapy administered to the patient
- The event does not follow a known pattern of response to study drug
- The event does not disappear or decrease on cessation or reduction in dose of the study drug, and it does not reappear or worsen when the study drug is re-administered

7.5 Adverse Events Qualifying for Reporting to Regulatory Authorities

The AEs that are serious and unexpected, and assessed as related to study drug, will be reported to the regulatory authorities by Forma Therapeutics, Inc. in accordance with local regulations. Serious, unexpected, and study drug-related events are to be reported to the regulatory authorities within 15 calendar days of initial notification to Forma Therapeutics, Inc. or its designee. If the AE is serious, unexpected, and related to study drug and is fatal or life threatening, the event will also be reported to the regulatory authorities within seven calendar days.

8 STUDY OR STUDY SITE TERMINATION AND PATIENT DISCONTINUATION

8.1 Study or Study Site Termination

If the Investigator, the Sponsor or Sponsor's Study Director or appropriate regulatory officials discover conditions arising during the study that indicate that the study should be halted or that the study center should be terminated, this action may be taken after appropriate consultation among the Sponsor, Investigator, and Study Monitor. Criteria that may be considered when determining a potential termination of the study would be unacceptable toxicity and/or an unfavorable risk-benefit profile.

Study termination and follow-up will be performed in compliance with the conditions set forth in the International Council on Harmonisation (ICH) sixth efficacy publication (E6) on Good Clinical Practice, Section 4.12, ICH E6 4.13, ICH E6 5.20, and ICH E6 5.21, with appropriate notification of the FDA and all IRB's/EC's having approved the study protocol and ICF.

8.2 Treatment and Study Discontinuation

8.2.1 Treatment Discontinuation

Study treatment discontinuation occurs when a patient is no longer receiving any study drug (FT-2102, azacitidine, or cytarabine, as applicable). Treatment discontinuation is not necessarily accompanied by discontinuation from the study, as discussed in Section 8.2.2.

A patient should be discontinued from study treatment if, in the opinion of the Investigator, doing so is medically necessary, or if it is the wish of the patient. Reasons for discontinuation from study treatment may include any of the following:

- Unacceptable AE or failure to tolerate study therapy
- Delay in dosing of > 28 days, without approval of Sponsor
- Treatment failure (i.e., progression or relapse) (see Section 4.3, Table 3 for definition)
- Hematopoietic stem cell transplant (HSCT)
- Withdrawal of consent (no further study participation)
- Patient decision to discontinue study treatment
- Discretion of the Investigator
- Major protocol violation
- Pregnancy
- Lost to follow-up
- Death
- Termination of the study by Sponsor

All AEs leading to the discontinuation of study drug will be followed for 28 days after administration of last dose of study drug or until resolution or stabilization as documented by physical examination or appropriate laboratory results.

All patients who discontinue study treatment should undergo the End-of-Treatment assessments (see Section 6.1.23) and undergo Safety Follow-up (Section 6.1.24)/ enter Survival Follow-up (Section 6.1.26).

Patients who discontinue study treatment for reasons other than disease progression/relapse, including those who discontinue for HSCT, will continue to be followed for response duration until progression/relapse occurs (see Section 6.1.25).

Patients who discontinue treatment for HSCT should continue to be assessed for response as per the protocol-defined schedule.

8.2.2 Study Discontinuation

Patients may voluntarily withdraw from the study at any time for any reason without prejudice. Patients will be withdrawn from the study in the case of any of the following reasons:

- Death
- Lost to follow-up
- Completion of follow-up period
- Termination of the study by Sponsor
- Withdrawal of consent

9 DATA RECORDING, CRF PROCESSING, AND STATISTICAL ANALYSIS

9.1 Data Recording and CRF Processing

In place of recording patient data on paper CRFs, which will not be used in this study, site personnel are responsible for entering such data into the Electronic Data Capture (EDC) system. This system has been validated and is compliant with FDA, ICH, and European Union (EU) regulations and guidelines and with Department of Health and Human Services 21 CFR Part 11 rules for electronic records and electronic signatures. No data will be requested other than what is routinely written on paper CRFs.

An audit may be performed at any time during or after completion of the clinical study by Sponsor personnel or their designee. All study-related documentation must be made available to the designated auditor.

9.2 Statistical Analysis

9.2.1 General Considerations

Unless otherwise specified, continuous endpoints will be summarized with n, mean, standard deviation (SD), median, minimum (min), and maximum (max). If the measurements in the source (raw) data are integers, then the corresponding mean and median will be presented to 1 decimal place and the SD to 2 decimal places; if the measurements are obtained to 1 decimal place, then the mean and median will be presented to 2 decimal places and the SD to 3 decimal places; and so forth. Minimum and maximum will be displayed as reported in the source (raw) data. In addition, change from baseline values will be calculated at each timepoint and summarized descriptively. For categorical endpoints, descriptive summaries will include counts and percentages. Percentages will be presented to 1 decimal place unless otherwise specified.

All analyses and summary outputs will be generated using SAS® version 9.3 (or higher).

All patient data, including those derived, will be presented in the patient data listings; listings will display for all patients, regardless of whether or not they received study drug. In general, the patient data listings will be sorted by treatment (dose levels), patient number and assessment visit and date (and time, if applicable). The summary tables will be presented descriptively overall and by treatment group.

For the purpose of all safety and efficacy analyses where applicable, baseline is defined as the last non-missing measurement prior to the start of study drug administration.

9.2.2 Sample Size

Sample size calculations are based on the primary objectives for each study cohort.

9.2.2.1 Phase 1

The primary objective for Phase 1 in this study is to evaluate DLT or identify MTD/MED and recommend a dose for Phase 2. Within the Phase 1 portion of the study, the Dose-Escalation Stage is based on a traditional 3+3 design to avoid selection of a dose going forward in development that causes a treatment-limiting toxicity in more than 17% of patients. At each dose level, 3 patients will be enrolled; if < 1/3 DLTs are identified, the dose will be escalated to the next dose level. If 1 DLT is identified, 3 additional patients will be added to the same dose level. If 1/6 DLT is identified, the study will be escalated to the next dose level. Otherwise, the MTD will be identified as the dose lower than the dose with > 1/6 DLTs.

The total number of patients who will be enrolled in the dose-escalation stage will depend on the number of DLTs observed within each dose cohort. It is anticipated that, at a minimum, doses of 150 mg and 300 mg FT-2102 QD will be tested as a single agent and in combination with azacitidine. If 6 patients are treated at each dose level, approximately 24 patients will be treated in the dose-escalation stage.

During the Phase 1 Dose-Expansion Stage, each of the non-LDAC cohorts would have 14 patients. With 20 patients treated (at least 6 from the dose-escalation stage, 14 from dose-expansion) at the determined MTD/MED, the probability of observing at least 1 incidence is > 87% for adverse events of true incidence rate of ≥17%. For the LDAC cohort, the selection of 6 patients is a minor variation of the traditional 3+3 design in order to identify the risk of LDAC for toxicities in more than 17% of patients.

9.2.2.2 Phase 2

The primary objective of Phase 2 is to evaluate the clinical activities of FT-2102 alone or in combination in patients with R/R AML or MDS and confirmed IDH1 mutation.

Cohort 1 (patients with R/R AML harboring IDH1-R132 mutations): A group sequential design is planned for this cohort with two interim analyses and a final test. One hundred seventy three (173) patients provide 90% power to test the null hypothesis that the true complete response rate (CR + CRh) is 15% or less versus the one-sided alternative hypothesis that the true complete response rate is greater than 15%, with a 2.5% significance level using a one-sided exact test for a binomial proportion, assuming the true response rate is 25%.

Two interim analyses are planned, at approximately 33% and 67% of the information. O'Brien-Fleming stopping boundaries will be used for both alpha and beta adjustments. At the first interim, if $\leq 6/58$ responses are observed (or crude p-value ≥ 0.88), the trial may be stopped early for futility. The first interim analysis will be conducted on the Full Analysis Set (FAS) within Phase 2 Cohort 1. At the first interim analysis, the study is not intended to stop for efficacy. At the second interim analysis, if $\geq 28/115$ responses are observed (or crude p-value is ≤ 0.0057), the trial may stop enrollment for efficacy and if there are 20 or fewer responses (or crude p-value is ≥ 0.2718) the trial may be stopped for futility. The second interim analysis will be conducted

in the Efficacy Evaluable (EE) Set within Phase 2 Cohort 1. In the event of an early stop for efficacy, all enrolled patients would remain on treatment and their long-term efficacy data, such as EFS and OS, will continue to be observed.

If the study is not stopped early for efficacy or futility, at least 173 evaluable patients are planned to be enrolled. A one-sided exact test will be performed. If the one-sided p-value is ≤ 0.0245 , the null hypothesis (the response rate is $\leq 15\%$) will be rejected, and the alternative hypothesis that the response rate is $\geq 15\%$ will be accepted. If exactly 173 patients are evaluable, this is equivalent to 36 or more responses observed.

To account for potential discordance between central and local testing of the IDH1-R132 mutation, approximately 190 patients are planned to be enrolled into this cohort.

Cohort 2 (patients with AML with persistent IDH1-R132 mutation + bone marrow demonstrating morphologic CR/CRi after prior therapy +/- HSCT): A Simon optimal two-stage design will be used. The null hypothesis that the true 4-month RFS rate is 80% will be tested against a one-sided alternative. In the first stage, 11 patients will be evaluated. If 9 or fewer of the first 11 patients are relapse-free at 4 months, the study will be stopped. Otherwise, 42 additional patients will be accrued, for a total of 53 patients. The null hypothesis will be rejected if 48 or more of these 53 patients are event-free at 4 months. This design yields a 1-sided type I error rate of 0.025 and power of 80% when the true 4-month RFS rate is 94%.

Cohorts 3-5 (patients with AML/MDS harboring IDH1-R132 mutations that are R/R to prior IDH1 inhibitor therapy; or naïve to hypomethylating and IDH1m inhibitor treatments; or R/R to prior hypomethylating therapy): A single-stage design with 20 patients will be used. If 4 or more complete responses are observed in these 20 patients, the lower bound of a one-sided 85% confidence interval based on an exact binomial distribution will be greater than 10%, thus supporting the hypothesis that the true complete response rate is greater than 10%.

Cohort 6 (patients with AML/MDS harboring IDH1-R132 mutations that are R/R to immediately prior SA IDH1 inhibitor therapy): A Simon's optimal two-stage design will be used. The null hypothesis that the true complete response rate is 15% will be tested against a one-sided alternative. In the first stage, 14 patients will be evaluated. If there are 2 or fewer complete responses in the first 14 patients, the study will be stopped. Otherwise, 30 additional patients will be accrued for a total of 44 patients. The null hypothesis will be rejected if 11 or more complete responses are observed in these 44 patients. This design yields a 1-sided type I error rate of 0.05 and power of 80% when the true complete response rate is 32%. The probability that the trial will be stopped at the end of the first stage if the true complete response rate is 10% is 0.65.

Cohort 7 (treatment naïve AML patients for whom standard treatments are contraindicated): A Simon's optimal two-stage design will be used. The null hypothesis that the true complete response rate is 25% will be tested against a one-sided alternative. In the first stage, 17 patients will be evaluated. If there are 5 or fewer complete responses in the first 17 patients, the study will be stopped. Otherwise, 37 additional patients will be accrued for a total of 54 patients. The null hypothesis will be rejected if 20 or more complete responses are observed in these 54 patients. This design yields a 1-sided type I error rate of 0.025 and power of 80% when the true complete response rate is 45%.

Cohort 8 (treatment naïve AML patients who are candidates for azacitidine first line treatment): A Simon's optimal two-stage design will be used. The null hypothesis that the true complete response rate is 25% will be tested against a one-sided alternative. In the first stage, 7 patients will be evaluated. If there are 2 or fewer complete responses in the first 7 patients, the study will be stopped. Otherwise, 21 additional patients will be accrued for a total of 28 patients. The null hypothesis will be rejected if 12 or more complete responses are observed in these 28 patients. This design yields a 1-sided type I error rate of 0.025 and power of 80% when the true complete response rate is 55%.

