2) Time variable CBD will be transformed to log form (LCBD) as below: LCBD=log(absolute value of CBD + 1)

- 3) A mixed model will be used to predict QOLtdi. The dependent variable is QOLtd; the mixed model will contain random intercept and slope subject effect, and fixed time effect (LCBD). QOLtdi will be predicted at imputed cycles.
- Compute QOLtdi re-transformed to the original scale (QOLback): This should be done by inverting the logistic regression equation.

QOLback = (logit(QOLt) - a)/b = [ln ((QOLt)/(1-QOLt)) - a]/b.

• Round imputed values up to the nearest whole number.

Note that no numerical values will be given after death, but "999" flags will be included to indicate cycles when patient was dead.

D. Multiple Study Centers

No stratification by the study centers will be utilized for analyses of efficacy or safety data.

E. Covariate Adjustment in Primary Analysis

Not planned for the primary analysis.

F. Sample Size Reassessment

No sample size reassessment is planned.

G. Interim Analyses

Interim analyses will be performed for the Phase 2 Cohort 1 and in other applicable Phase 2 cohorts that use two-stage designs, at defined timepoints, as outlined in section IV.C.

- Phase 2 Cohort 1: two interim analyses with 33% and 67% of patients' information respectively
- Phase 2 Cohort 2: with first 11 patients evaluable for response
- Phase 2 Cohort 6: with first 14 patients evaluable for response
- Phase 2 Cohort 7: with first 17 patients evaluable for response

• Phase 2 Cohort 8: with first 7 patients evaluable for response

As a result of these analyses, enrollment in a given cohort may be stopped early for futility, or in Cohort 1 for efficacy as well. Interim analyses that meet stopping criteria for futility are binding.

H. Multiple Comparisons

Alpha is controlled for the primary analysis within each Phase 2 cohorts. Corrections for multiple comparisons are not applied for the secondary or exploratory endpoints, as they are descriptive analyses.

I. Analysis Sets

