All patients in Phase 2, Cohort 1 with confirmed IDH1-R132 (by central lab) who have received the first dose of FT-2102 180 days or more prior to the analysis cutoff date. These patients will be included in the analysis set regardless of duration of treatment. This analysis set is the primary analysis set for Phase 2, Cohort 1 efficacy evaluation and early stopping decisions. Patients will be analyzed by assigned dose. Patients who received first dose of FT-2102 less than 180 days prior to the analysis cut off date will not be included in the EE Set, even if they have response assessments recorded. Patients who do not have any response data will be considered to be non-responders if they received the first dose of FT-2102 180 days or more before the analysis cut off date. Analyses based on the EE analysis set will not be produced for the final CSR.

5. Per Protocol (PP) Analysis Set

A subset of patients in the EE analysis set, excluding patients who have protocol violations that could impact the evaluation of the efficacy of FT-2102. Some violations that would result in exclusion from the PP analysis set are: not meeting all inclusion/ exclusion criteria for a particular cohort, having received chemotherapy not per protocol, received starting dose of FT-2102 other than 150 mg BID, not having at least one post-baseline response assessment. The full list of protocol violations will be reviewed on a de-identified basis by the medical, data management, and statistical leads prior to locking the database, and membership in the PP analysis set will be documented and determined based on that review. Analyses based on the PP analysis set will not be produced for the final CSR.

6. PK Analysis Set

All patients for whom it is possible to calculate at least one primary PK parameter (e.g. C_{max} , AUC_{last} and AUC_{inf}) and who do not have any major protocol deviations thought to influence the absorption, distribution, metabolism and excretion of the FT-2102.

PK parameters for patients who discontinue after a single dose of study drug may be presented in the listings but will not be used for summary statistics or any statistical analysis. Data may be excluded from PK analysis (concentrations listed only) if any of the following criteria are fulfilled:

- concomitant medication which could render the plasma concentration-time profile unreliable
- Patient vomits within 2 x the reported median T_{max} for the study drug.

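### Cohort 1's first futility look is run on a set with no minimum follow-up, while the SAP names the 180-day EE set for early stopping and contradicts itself on whether the stop is binding

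*Protocol*

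**What the plan says.** Protocol 9.2.2.2 sets up Cohort 1 as a group sequential design. On size it says: "One hundred seventy three (173) patients provide 90% power to test the null hypothesis". The null value is a CR/CRh rate of 15%, the assumed true rate is 25%, and the test is exact binomial, one-sided, at the 2.5% level. On timing it says: "Two interim analyses are planned, at approximately 33% and 67% of the information". At the first look (IA1) the futility threshold is 6 or fewer responses in 58, and SAP IV.C says that this look spends no alpha and 0.004 beta.

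On the analysis set for IA1 the Protocol says "The first interim analysis will be conducted on the Full Analysis Set (FAS) within Phase 2 Cohort 1", and SAP IV.C says the same. Both assign the second look (IA2) to the EE set. The FAS (Protocol 9.2.3, SAP VI.I.3) takes everyone enrolled who had at least one dose of FT-2102. It has no minimum follow-up and does not require central IDH1 confirmation.

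SAP VI.I.4 defines the EE set as centrally confirmed Cohort 1 patients first dosed 180 days or more before cut-off, and leaves out later starters even if they have been assessed. It adds: "This analysis set is the primary analysis set for Phase 2, Cohort 1 efficacy evaluation and early stopping decisions".

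On the force of the rule, SAP VI.G says "Interim analyses that meet stopping criteria for futility are binding". Protocol 9.2.2.2 and SAP IV.C say only that the trial *may* stop at IA1. SAP IV.C uses *will* for futility at IA2.

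**The concern.** The endpoint is best overall response of CR or CRh, and under Protocol 4.3 and SAP XI.A the first on-treatment marrow is at C2D1 or C3D1, roughly 4 to 8 weeks after first dose. A patient dosed shortly before the IA1 cut-off cannot yet be a responder, but belongs to the FAS and so sits in the denominator of 58 as a non-response.

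Nothing in 9.2.2.2, SAP IV.C or SAP VI.G prevents this. The trigger is a fraction of the information and nothing more. The other two-stage cohorts are treated differently: SAP VI.G counts patients evaluable for response, and the Protocol synopsis ties the looks in Cohorts 2 and 6 to completion of the first response assessment.

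At stake is the chance of stopping the largest Phase 2 cohort for futility when the drug has the effect the trial was powered to find. The team also cannot follow SAP IV.C and SAP VI.I.4 together at IA1 without choosing between them.

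**Working it through.** **Inputs from the documents.** Null rate 15%, alternative 25%; looks at 58, 115 and 173 patients; futility at 6 or fewer (IA1) and 20 or fewer (IA2); efficacy at 28 or more (IA2) and 36 or more (final). All are in Protocol 9.2.2.2 and SAP IV.C.

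**Input that is assumed.** f, the share of eventual CR/CRh among the 58 already visible at IA1. The documents give no value; 100% down to 50% is shown.

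**1. Reproduce the stated design.** Exact upper tail probabilities at 15%: 6/58 gives 0.885 (stated 0.88), 28/115 gives 0.0057, 20/115 gives 0.2718 and 36/173 gives 0.0245. All agree with the plan.

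At 25%, P(X ≤ 6), X ~ Bin(58, 0.25), is 0.0046. O'Brien-Fleming type spending of beta 0.10 at t = 58/173 = 0.335 is 2[1 − Φ(1.645/√0.335)] = 0.0045. The stated 0.004 is therefore the risk when all 58 outcomes are known.

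Exact recursion over the three looks, with both futility rules applied, gives power 90.7% and type I error 2.45%. The design is sound on mature data.

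**2. Let some responses be unseen at IA1.** Let T ~ Bin(58, 0.25) be the eventual responders among the 58. Each is visible at IA1 with probability f, so the observed count is O | T ~ Bin(T, f), and O ~ Bin(58, 0.25f) overall.

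- False stop = P(O ≤ 6).
- Power = sum over t of P(T = t) × P(O > 6 | t) × P(reject at IA2 or final | T = t), with all eventual responses counted from IA2 onwards.

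| f | Observed rate 0.25f | False stop at IA1 | Overall power |
|---|---|---|---|
| 100% | 25.0% | 0.46% | 90.7% |
| 95% | 23.75% | 0.8% | 90.5% |
| 90% | 22.5% | 1.4% | 90.2% |
| 80% | 20.0% | 4.0% | 88.5% |
| 70% | 17.5% | 9.8% | 83.9% |
| 60% | 15.0% | 21.4% | 74.1% |
| 50% | 12.5% | 40.1% | 57.2% |

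The table treats the stop as automatic. Put another way, if k of the 58 cannot yet be assessed and the rest are mature, the false stop is P(Bin(58 − k, 0.25) ≤ 6): 2.7% for k = 10, 6.1% for k = 15 and 12.8% for k = 20.

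**3. Central discordance alone.** The enrolment allowance is (190 − 173)/190 = 17/190 = 8.9%. If none of those patients respond, the FAS rate is 0.25 × 173/190 = 0.228 and the false stop is 1.3%. Missing follow-up is what matters.

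**4. Type I error.** Hidden responses at IA1 can only add futility stops. At a true 15% the rejection probability falls from 2.45% (f = 100%) to 1.15% (f = 50%).

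**5. Binding or not.** With IA1 non-binding and IA2 futility kept, type I error is 2.46% and power 90.8%. With both futility rules ignored, type I error is 2.59%, above 2.5%.

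**The case against.** Five points can be made for the plan.

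- **The choice of set is deliberate and consistent.** Protocol and SAP both name the FAS for IA1 and the EE set for IA2. A reader might infer that the SAP reserves early stopping for the EE set, so that the FAS is barred. The text does not go that far: VI.I.4 calls the EE set primary for these decisions, and IV.C is a specific rule for one look. This stands, but the general sentence and the specific rule still disagree, and VI.I.4 carves out no exception.
- **The stop may be discretionary.** A reader might take VI.G alone and conclude that a false stop would be automatic. The two sections that set the IA1 threshold say *may*, and a team free to judge could look at follow-up first. This stands as a limit on the power figures, which all assume an automatic stop.
- **The size depends on an assumed share.** Also true. With 90% or more visible the false stop is at most 1.4% and power stays above 90%, so the stated power does not require complete maturity. The serious figures begin at about 70%, which the text does not rule out.
- **A trigger may exist elsewhere.** The synopsis paragraph on Cohort 1 sample size was not in the text available for this review, so a follow-up condition stated only there cannot be excluded. Protocol 9.2.2.2 and SAP IV.C and VI.G contain none.
- **The look appears to be past.** The SAP version 5.0 change summary refers to analyses performed for a pivotal IA2. A changed rule cannot alter a look already taken, but how it was done still needs reporting.

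**Conclusion.** The point holds as a conflict between stated decision rules, with a consequence for power that may be small or large. Read literally, IA1 can count patients who have had no chance to respond as failures; the SAP names a different, mature set for the same kind of decision; and the documents disagree on whether the result compels a stop.

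The stated beta spend at IA1 is correct for 58 mature outcomes only. If the stop is binding and the true rate is 25%, the false-stop risk runs from 0.8% with 95% of eventual responses visible, through 4.0% with 80%, to 40.1% with 50%. The documents do not allow a choice within that range.

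A reader might infer that the 90% power claim is wrong, that a positive result is in doubt, or that unconfirmed mutations drive the problem. None follows: power is 90.7% on mature data and 90.2% with 90% visible, type I error falls rather than rises, and discordance alone gives 1.3%. This should be fixed; it is not a fatal flaw.

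**What to change.** - **Set and follow-up.** In Protocol 9.2.2.2 and SAP IV.C, state that the 58 IA1 patients are the first 58 Cohort 1 FAS patients first dosed at least 180 days before cut-off. IV.C and VI.I.4 then agree on follow-up. Central confirmation is not essential at this look; a short clause in VI.I.4 can say so. With mature outcomes the false stop returns to 0.46%, with power 90.7% and type I error 2.45%.
- **Which definition.** Use the SAP's timing rule, not the EE definition in Protocol 9.2.3. The latter admits patients with under 6 months who died, progressed or discontinued, but omits equally recent patients still on study, which biases the rate downwards.
- **Binding status.** Reconcile *may* in 9.2.2.2 and IV.C with the binding statement in VI.G for IA1. Making IA1 alone non-binding keeps type I error at 2.46%. Do not extend that to IA2 without rechecking, since ignoring both futility rules gives 2.59%.
- **If IA1 has been done.** Report its data cut-off, the follow-up of the 58 patients, the set used and the rule applied.

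The cost is about a sentence in each place and a later futility look, with more patients enrolled by then. Requiring a completed first response assessment, as for Cohorts 2 and 6, would delay the look less. It would remove patients with no assessment at all, but would still miss later responses and would not match VI.I.4.
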